### 9.2.1. Inclusion Criteria

Data for this interim analysis are derived from the ongoing C4591036 study, "Low-interventional Study of Myocarditis and Pericarditis Associated with COMIRNATY in Persons Less Than 21 Years of Age." The following inclusion criteria are used for eligibility in the C4591036 study:

Patients must meet all of the following inclusion criteria to be eligible for inclusion in the study:

[figure not shown]
Cohort 1 (prospectively ascertained) and Cohort 2 (retrospectively ascertained): Cases of probable or confirmed myocarditis/pericarditis associated with COMIRNATY

- 1. Age <21 years
- 2. Presentation to a participating medical center with evaluation in Emergency Room and/or hospitalization
- Received either the 1st, 2nd, 3rd, or booster dose(s) of COMIRNATY ≤21
  days of symptom onset, even if a different brand of COVID-19 vaccine had
  been administered in earlier vaccinations. Participants can be retrospectively

[figure not shown]
- ascertained and enrolled at any time from their COMIRNATY-associated myocarditis/pericarditis.
- 4. Probable or confirmed myocarditis/pericarditis as per the contemporaneous CDC case definition (Table 3)\*11-12 at the time of diagnosis.
- 5. Capable of giving signed informed consent/assent (by parents/legal guardians of minors and/or patients) as described in (see protocol), which includes compliance with the requirements and restrictions listed in the Informed Consent/Assent Document and in this protocol OR meets criteria for waiver of consent.

## Table 3. CDC Working Case Definitions

Centers for Disease Control and Prevention Working Case Definitions for Acute Myocarditis, Pericarditis, & MIS-C

## **Acute Pericarditis Probable Case** • Presence of $\geq 2$ new or worsening of the following clinical features: acute chest pain pericarditis rub on exam new ST-elevation or PR-depression on ECG new or worsening pericardial effusion on echocardiogram or MRI · Autopsy cases may be classified as pericarditis on basis of meeting histopathologic criteria of the pericardium

Adapted from Centers for Disease Control and Prevention. Copyright ©2021, Centers for Disease Control and Prevention.

Abbreviations: cMRI = cardiac magnetic resonance imaging; ECG = electrocardiogram.

\* Persons who lack the listed symptoms but who meet other criteria may be classified as subclinical myocarditis (probable or confirmed).

- † Using the Dallas criteria. Autopsy cases may be classified as confirmed clinical myocarditis on the basis of meeting histopathologic criteria if no other identifiable cause. § To meet the ECG or rhythm monitoring criterion, a probable case must include at least one of 1) ST-segment or T-wave abnormalities; 2) Paroxysmal or sustained atrial, supraventricular, or ventricular arrhythmias; or 3) AV nodal conduction delays or intraventricular conduction defects, excluding first degree AV block, Mobitz Type I (Wenkebach), and incomplete right bundle branch block.
- ¶ Using either the original or the revised Lake Louise criteria.

  †† Typically described as pain made worse by lying down, deep inspiration, or cough, and relieved by sitting up or leaning forward, although other types of chest pain might occur.

\*This table is adapted from Bozkurt et al (2021) and the Centers for Disease Control and Prevention. 11-14

# Cohort 3: Comparator cohort of COVID-19-related myocarditis/pericarditis, including MIS-C

- 1. Age <21 years
- 2. Presentation to a participating medical center with evaluation in an Emergency Room and/or hospitalization
- COVID-19-related disease
  - a. Acute COVID-19 infection based on characteristic signs and symptoms, together with a positive microbial test (either a positive nucleic acid amplification test (NAAT), most commonly with a reverse-transcription polymerase chain reaction (RT-PCR) assay, or an antigen test on an upper respiratory sample)

OR

b. Multi-system Inflammatory Syndrome in Children Associated with COVID- 19 (MIS-C) as per the contemporaneous CDC case definition at the time of diagnosis, i.e. participants diagnosed with MIS-C prior to 01 Jan 2023 should follow the original (May 2020) CDC case definition, and those diagnosed with MIS-C on or after 01 Jan 2023 should follow the new case definition.

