### 9.2.2. Exclusion Criteria

Participants are excluded from the study if any of the following criteria apply:

- 1. A plausible alternative etiology for myocarditis/pericarditis, as determined by the site based upon their routine clinical practice for evaluation of potential causes for myocarditis/pericarditis.
- 2. Pre-existing cardiac conditions that could impact the primary endpoint, including but not limited to, documented history of left ventricular dysfunction (e.g., cardiomyopathy or myocardial infarction), pacemaker, or congenital heart disease, with the exceptions of:
  - a. Bicommissural aortic valve with ≤ trivial stenosis and/or insufficiency
  - b. Mitral valve prolapse with ≤ trivial insufficiency
  - c. Hemodynamically insignificant atrial septal or ventricular septal defects
- 3. Previous administration with an investigational drug or vaccine within 30 days of enrollment (or as determined by the local requirement)

Patients who do not meet the criteria for participation in this study (screen failure) may be rescreened. For example, if a patient is considered for enrollment after first vaccination but fails to meet admission criteria, he or she could still be rescreened if symptoms occur after the second vaccine or booster.

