#### 9.9. Limitations of the Research Methods

As C4591079 utilizes data from C4591036, potential limitations are common to both studies and should be noted:

- Because of the decline in number of COMIRNATY-associated myocarditis cases (according to the Vaccines Adverse Events Reporting System [VAERS], cases reported in the US reached a peak in June 2021 and dropped dramatically after October 2021), the myocarditis/pericarditis cohort is largely comprised of retrospectively ascertained cases.
- Patients will be excluded from participation if plausible etiologies for myocarditis other than COMIRNATY-associated myocarditis are known at enrollment. It is possible that a plausible alternative etiology will be discovered only after a participant is enrolled. If so, those participants will be followed per C4591036 but will be accounted for separately in the statistical analysis.
- Some individuals who had COMIRNATY-associated myocarditis/pericarditis
  prior to the start of the study period may decline consent/assent or be difficult to
  reach. Each clinical center enrolling under C4591036 will work closely with
  pediatric offices to maximize return for scheduled visits. Participants who have
  returned to normal health and cardiac status may also be less inclined to return
  for follow-up at the recommended time points.
- A waiver of consent can be requested for collection of information related to clinical care when clinical sites are unable to reach participants with a history of vaccine myocarditis/pericarditis or COVID-19-related myocarditis/pericarditis, including MIS-C. In such patients, data collection will be limited to "retrospective" medical records review, including images obtained in the course of clinical care. No activities that are solely research-related are obtained or required.
- CMRIs are performed only when ordered as part of routine clinical care, and there may be practice variation among centers/providers regarding timing and protocols for cMRI.
- The COMIRNATY myocarditis and comparison participants are symptomatic
  patients evaluated and diagnosed in medical centers. They will not include
  individuals in the community with subclinical myocarditis/pericarditis. The study
  population will only include those with clinical myocarditis/pericarditis. Therefore,
  results from this study cannot be generalized to those in a subclinical
  myocarditis population.

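### Inclusion criteria for the vaccine and COVID-19 cohorts overlap, and a patient with both exposures is handled only by a site-judged exclusion that names neither

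*Protocol*

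**What the plan says.** Secondary objective 2 (Section 8) compares acute and long-term cardiac outcomes between COMIRNATY-associated cases and cases associated with COVID-19, including MIS-C. Four places in the protocol decide who stands on each side.

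- **Section 9.2.1, Cohorts 1 and 2, criterion 3:** the patient "Received either the 1st, 2nd, 3rd, or booster dose(s) of COMIRNATY" within 21 days of symptom onset. A negative SARS-CoV-2 test or absence of MIS-C is not required.
- **Section 9.2.1, Cohort 3, criterion 3:** either "Acute COVID-19 infection based on characteristic signs and symptoms, together with a positive microbial test", or MIS-C "as per the contemporaneous CDC case definition at the time of diagnosis". Nothing is said about a recent COMIRNATY dose, and no interval is set between the positive test and the cardiac findings.
- **Section 9.2.2, exclusion 1:** "A plausible alternative etiology for myocarditis/pericarditis, as determined by the site based upon their routine clinical practice". It applies to all participants and names neither COVID-19 nor vaccination.
- **Section 9.9:** "Patients will be excluded from participation if plausible etiologies for myocarditis other than COMIRNATY-associated myocarditis are known at enrollment". It goes on: "It is possible that a plausible alternative etiology will be discovered only after a participant is enrolled", in which case the participant stays in follow-up but is accounted for separately in the analysis.

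Table 4 collects vaccine dates and brands in all three cohorts. It also collects prior SARS-CoV-2 infection, with an approximate date and the method of ascertainment. Section 9.5 sets the interim cohort at 200 vaccine-associated and 100 COVID-associated participants.

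**The concern.** The groups in objective 2 are defined by presumed cause, but their inclusion criteria are two exposures that can occur in the same person. Someone vaccinated 10 days before onset who also tests positive, or meets the MIS-C definition, satisfies the inclusion lists of both sides. Whether that person is excluded, and otherwise which group they join, depends on how the site reads exclusion 1.

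If sites read it differently, exposure is misclassified in the variable that defines the comparison. If dual-exposed patients in Cohort 3 carry the risk of vaccine cases, the contrast shrinks. If sites sort such patients by severity, the direction of the error is unknown. Site judgement is also hard to standardise here: Cohorts 2 and 3 may be ascertained retrospectively, at any time after the episode, and may include patients under a waiver of consent for whom only medical records are reviewed (Section 9.2).

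**Working it through.** **Step 1: set the criteria side by side for a dual-exposed patient** (COMIRNATY within 21 days before onset, plus acute COVID-19 or MIS-C at the same episode).

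| Rule | Cohorts 1/2 | Cohort 3 |
|---|---|---|
| Exposure criterion in 9.2.1 | met by the dose | met by the positive test or MIS-C |
| Bar on the other exposure in 9.2.1 | none | none |
| Exclusion 1 in 9.2.2 | can exclude, if the site regards COVID-19 or MIS-C as a plausible alternative cause | can exclude, if the site regards the recent dose as a plausible alternative cause |
| Stated assignment rule | none | none |

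The overlap therefore lies in the inclusion criteria. Exclusion 1 can close it on either side, but only through site judgement. The footnote to Table 4 defines post-vaccine cohorts by the 21-day dose alone, so a Cohort 3 participant with such a dose would also fit the description of the exposed group.

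**Step 2: size of the effect.** The protocol gives no dual-exposed count, no composite rates and no planned effect size, so there is no figure of its own to reproduce. All rates and overlap shares below are assumptions.

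Let pV and pC be the true composite rates for vaccine and COVID-19 cases, and f the share of Cohort 3 that is dual-exposed with vaccine-like risk.

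- Observed Cohort 3 rate = (1 − f) × pC + f × pV
- Observed difference = (1 − f) × (pC − pV)

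| f | Difference, pV = 10%, pC = 20% | Difference, pV = 10%, pC = 30% |
|---|---|---|
| 0 | 10.0 points | 20.0 points |
| 2% | 9.8 | 19.6 |
| 5% | 9.5 | 19.0 |
| 10% | 9.0 | 18.0 |
| 20% | 8.0 | 16.0 |

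Example: f = 10% gives 0.90 × 0.20 + 0.10 × 0.10 = 0.19, and 0.19 − 0.10 = 0.09.

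If a share g of Cohorts 1/2 is also dual-exposed and carries COVID-like risk, the observed difference is (1 − f − g) × (pC − pV). With f = g = 5% and 10% versus 20%, this is 0.90 × 10 = 9 points.

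**Step 3: compare with sampling error**, assuming complete data on 200 and 100.

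- 10% versus 20%: 1.96 × √(0.10 × 0.90/200 + 0.20 × 0.80/100) = 1.96 × √0.00205 = 8.9 points
- 10% versus 30%: 1.96 × √(0.10 × 0.90/200 + 0.30 × 0.70/100) = 1.96 × √0.00255 = 9.9 points

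At 10% overlap the bias is 1 point (10% versus 20%) or 2 points (10% versus 30%), well inside these half-widths.

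**Step 4: dependence on the risk assumption.** If dual-exposed patients in Cohort 3 carry COVID-like risk, there is no dilution. If their risk exceeds both, say 30% with f = 10% and 10% versus 20%, Cohort 3 reads 0.90 × 0.20 + 0.10 × 0.30 = 21% and the difference grows to 11 points. The direction is therefore not fixed by the documents.

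**The case against.** The strongest reply is that eligibility means inclusion plus exclusion. Exclusion 1 is not limited to any cohort and on its plain wording works in both directions. This stands: a reader might infer from the inclusion lists that a dual-exposed patient is fully eligible for both sides, and the documents do not support that. What remains is that the exclusion is discretionary and names neither exposure.

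A reader might also infer from Section 9.9, with its phrase "plausible etiologies for myocarditis other than COMIRNATY-associated myocarditis are known at enrollment", that COVID-19 keeps a patient out of the vaccine cohorts while a recent dose never keeps one out of Cohort 3. That does not hold. Applied literally to every cohort, the sentence would exclude all of Cohort 3, whose cause is COVID-19. It makes sense only as a description of the vaccine cohorts, in a limitations list, and cannot narrow the operative criterion. The wording is loose and worth correcting, but it is not evidence of a one-way rule.

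A third inference, that some people are counted twice, is not shown either: Section 9.5 divides 300 participants into 200 and 100.

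Section 9.9 also has a second safeguard, separate accounting for alternative causes found after enrollment. It does not reach a dual exposure known at enrollment that the site chose not to treat as an alternative cause.

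Finally, these participants were enrolled under C4591036 by mid-April 2025, before this protocol's date of July 31, 2025, and Section 9.7 leaves detailed methods to a SAP that is not at hand. Eligibility cannot be changed retrospectively, and the SAP may already handle dual exposure. But the cohort definitions and the interim analysis set are fixed in this protocol, and an analysis-set rule needs no change to enrollment.

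**Conclusion.** The point holds as a gap in how the compared groups are defined. The two inclusion lists overlap, no assignment rule is stated, and the one criterion that could separate the groups is left to site practice. Some dual-exposed cases may remain in either group, including the comparator.

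The effect is probably small unless overlap is substantial. On the assumed 10% versus 20%, overlap of 10% to 20% in Cohort 3 costs 1 to 2 points of a 10-point difference, against a half-width of about 8.9 points. Those figures rest on assumed rates, an assumed overlap and vaccine-like risk in the dual-exposed; the documents supply none of these. The analysis is descriptive, so no power statement is affected. The case for acting is that a confidence interval does not reflect misclassification of this kind, its direction is uncertain, and most of the data needed to measure it are already collected. It is worth changing but does not undermine the study.

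**What to change.** In Section 9.5, for the interim analysis set:

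1. Flag any participant with a COMIRNATY dose within 21 days before onset and acute COVID-19 or MIS-C at the index episode. Use the vaccine dates in Table 4 and the qualifying test or diagnosis. The infection dates in Table 4 are only approximate and should not carry the flag alone.
2. Report the number flagged, by enrolled cohort.
3. Describe flagged participants separately, as Section 9.9 already provides for alternative causes found after enrollment.
4. Leave them out of the main objective 2 comparison, and add a sensitivity analysis that keeps them in their enrolled cohort.

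In Section 9.9, reword the bullet so that it describes exclusion 1 for all cohorts. If the SAP already contains an equivalent rule, a cross-reference in Section 9.5 is enough.

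The cost is a short paragraph, one derived variable and the loss of a few participants from the main comparison. One limit remains: Cohorts 1 and 2 have no qualifying SARS-CoV-2 test, so the flag will be less complete there than in Cohort 3, and the report should say so.

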### AND

- 4. Probable or confirmed myocarditis/pericarditis as per the contemporaneous CDC case definition (See Table 3)\*11-12 at the time of diagnosis.
  - a. Probable myocarditis/pericarditis as defined by ≥1 new finding of:
    - a. Elevated troponin above upper limit of normal
    - b. Abnormal ECG or rhythm monitoring finding consistent with myocarditis, excluding those in whom the sole abnormality was first degree atrioventricular (AV) block
    - c. Abnormal cardiac function or wall motion abnormalities on echocardiogram
    - d. cMRI findings consistent with myocarditis

### OR

- b. Confirmed myocarditis/pericarditis as defined by:
  - a. Histopathologic confirmation of myocarditis

### OR

- b. Elevated troponin above upper limit of normal AND cMRI findings consistent with myocarditis
- Capable of giving signed informed consent/assent (by parents/legal guardians of minors and/or patients), which includes compliance with the requirements and restrictions listed in the Informed Consent/Assent Document and in this protocol OR meets criteria for waiver of consent.

### 9.2.2. Exclusion Criteria

Participants are excluded from the study if any of the following criteria apply:

- 1. A plausible alternative etiology for myocarditis/pericarditis, as determined by the site based upon their routine clinical practice for evaluation of potential causes for myocarditis/pericarditis.
- 2. Pre-existing cardiac conditions that could impact the primary endpoint, including but not limited to, documented history of left ventricular dysfunction (e.g., cardiomyopathy or myocardial infarction), pacemaker, or congenital heart disease, with the exceptions of:
  - a. Bicommissural aortic valve with ≤ trivial stenosis and/or insufficiency
  - b. Mitral valve prolapse with ≤ trivial insufficiency
  - c. Hemodynamically insignificant atrial septal or ventricular septal defects
- 3. Previous administration with an investigational drug or vaccine within 30 days of enrollment (or as determined by the local requirement)

Patients who do not meet the criteria for participation in this study (screen failure) may be rescreened. For example, if a patient is considered for enrollment after first vaccination but fails to meet admission criteria, he or she could still be rescreened if symptoms occur after the second vaccine or booster.

### 9.3. Variables

Variables collected in this study including their role, data source, and operational definition are summarized in Table 4.

**Table 4. Study Variables** 

Variable	Role	Data source(s)	Operational definition
Sociodemographic: Age, sex assigned at birth, gender identity (defined as one's self- identification as male, female, or other), race, ethnicity, insurance, zip code, census tract/dissemination area.	Predictors	Medical records; participant report	All study participants: post- vaccine* (Cohorts 1 and 2) and control participants (Cohort 3)
Dates and brand of 1st, 2nd, 3rd, or booster dose(s) of COVID-19 vaccine; type/name and Lot # of all COMIRNATY doses.	Exposure of interest	Medical records; participant report	All study participants: post- vaccine* (Cohorts 1 and 2) and control participants (Cohort 3)
Prior SARS-CoV-2 infection (symptomatic COVID-19 or asymptomatic): Yes/No. If yes, approximate date and method of ascertainment (e.g., positive RT- PCR, antigen, antibody, and/or exposure).	Predictors	Medical records; participant report	All study participants: post- vaccine* (Cohorts 1 and 2) and control (Cohort 3) participants

## **Table 4. Study Variables**

Variable	Role	Data	Operational definition
		source(s)	
Medical history: Date of admission, intensive care unit (ICU) stay, comorbid conditions including overweight and obesity by BMI (age-and sex-adjusted z scores using CDC [primary] and World Health Organization [WHO] [secondary] norms), prior doses and brands of COVID-19 vaccine administered before the COMIRNATY vaccine given within 7 days of myocarditis/pericarditis onset, prior history of myocarditis/pericarditis, clinical features at the time of presentation (e.g., chest pain, fever); type of shock if present (hypovolemic, distributive, cardiogenic); individual organ dysfunction at presentation; mechanical ventilation (date of intubation and first extubation, total days of intubation); ECMO, other serious medical events, death, discharge date.	Predictors	Medical records; participant report	All study participants: post-vaccine* (Cohorts 1 and 2) and control (Cohort 3) participants
Treatments for myocarditis/pericarditis or myopericarditis: Anti-inflammatory agents [e.g., intravenous immunoglobulins (IVIG), steroids, colchicine]; symptomatic treatments and analgesics [e.g., non-steroidal anti- inflammatory drugs (NSAIDs)]; antithrombotic (anticoagulants, antiplatelet agents), pressors, vasoactive agents, heart failure therapies [digoxin, diuretics, angiotensin converting enzyme (ACE) inhibitors, angiotensin II receptor blockers (ARBs), and procedural treatments (i.e., pacemaker, implantable cardiac defibrillator, mechanical circulatory support and heart transplantation].	Predictors	Medical records	All study participants: post-vaccine* (Cohorts 1 and 2) and control (Cohort 3) participants
Clinical Labs: Troponin	Predictors	Medical records	Per protocol, in post-vaccine* myocarditis/pericarditis (Cohorts 1 and 2): daily troponins (I or T in accordance with routine center clinical practice) while participants are

**Table 4. Study Variables** 

Variable	Role	Data	Operational definition
		source(s)	
			hospitalized or until levels have decreased for 2 successive measurements. If 2 consecutive troponin values have been normal in patients with no symptoms, further troponins are not mandatory per protocol. All study participants (Cohorts 1, 2, and 3): any troponin values that are obtained as part of routine clinical care.
Clinical Labs: BNP or NT-proBNP; c-reactive protein (CRP)	Predictors	Medical records	All study participants (Cohorts 1, 2, and 3): clinical labs obtained as part of routine clinical care
Electrocardiographic variables	Outcomes	Core laboratory	All study participants: post- vaccine* (Cohorts 1 and 2) and control (Cohort 3) participants
Echocardiographic variables	Outcomes	Core laboratory	All study participants: post- vaccine* (Cohorts 1 and 2) and control (Cohort 3) participants
Cardiac MRI variables	Outcomes	Core laboratory	Study participants for whom cMRI is performed as part of routine clinical care: post-vaccine* (Cohorts 1 and 2) and control (Cohort 3) participants
Exercise stress test variables	Outcomes	Medical records	Post-vaccine* (Cohorts 1 and 2); some control (Cohort 3) participants
Ambulatory monitoring	Outcomes	Medical records	Post-vaccine* (Cohorts 1 and 2); some control (Cohort 3) participants
Patient-reported outcome measures	Outcomes	Participant report	Post-vaccine* (Cohorts 1 and 2) and control (Cohort 3) participants
Complications and noncardiac morbidities	Outcomes	Medical records	Post-vaccine* (Cohorts 1 and 2) and control (Cohort 3) participants

\*Post-vaccine refers to cohorts receiving a dose of COMIRNATY ≤21 days from onset of myocarditis symptoms.

